#### 7.4.4. Overall Survival

Overall survival is defined as the time from the date of the first dose of study drug to death due to any cause. For participants who are still alive at the time of the analysis, OS will be censored on the date the participant is last known to be alive.

The number of participants who died and the number of participants censored will be summarized. The Kaplan-Meier estimate of median OS will be presented with its 95% CIs, with the CIs calculated using the generalization of Brookmeyer and Crowley's method (1982) with log-log transformation (Klein and Moeschberger 1997). Survival rates at 6, 12, 18, and 24 months will also be provided with 95% CIs calculated using Greenwood's formula to estimate the standard error.

#### 7.4.5. Best Percentage Change in Target Lesion Size

For participants in the FAS with measurable lesions at baseline, target lesion sizes will be measured by the sum of the product of diameters of all target lesions. The best percentage change from baseline, defined as the largest decrease in target lesion sizes on/before new anti-lymphoma therapy during the study, will be summarized. A waterfall plot of the best percentage change will be generated using data from the IRC. Note that for participants who

only have increases in target lesion sizes from baseline, the smallest increase will be considered as the best change from baseline. For the IRC, 2 radiologic reviewers will conduct separate reviews for each participant. An adjudication will be performed per the Independent Review Charter when Reviewers 1 and 2 disagree on the CT/MRI best overall response, or when best overall response is consistent, but the date of initial response and/or the date of progression differ between Reviewers 1 and 2. The adjudicator will select the read that he or she believes more accurately reflects the adjudication parameter(s) in question. This is considered the "accepted read," and data from this reviewer will be used for the analysis. When there is no adjudication needed, data from Reviewer 1 will be used for the analysis. An indicator will be provided to identify the read that is considered to be the accepted assessment in data from the IRC.

Best change in target lesion size as reported by the investigator will also be summarized as described above. Target lesions considered "too small to measure" will be assigned a default value of 5 mm × 5 mm for purposes of this analysis. Likewise, target lesions identified as "not present" at postbaseline assessments will be assigned 0 mm × 0 mm for this analysis. In the event that a target lesion is unaccounted for in a particular postbaseline timepoint (ie, the assessment is missing or NE), then the overall sum of target lesions will not be evaluable for that postbaseline timepoint.

### **7.5.2. Other Efficacy Analyses**

For investigator-reported responses, sites will use the CT-based response criteria of the Lugano Classification ([Cheson et al 2014](#)) to assess response to treatment locally. At each postbaseline disease assessment, responses will be collected in the eCRF as CR, PR, SD, PD, or NE. The best overall response is the best response recorded before and including the first PD, in the order of CR, PR, SD, PD, and NE. The best overall response will be determined from response assessments on or before the start date of new anticancer therapy. In the case of SD, assessment must meet the SD criteria at least once on or after Day 42. Participants who fail to meet this criterion will have best response of PD if the next available assessment after the initial assessment indicates PD or will have best response of NE if there are no additional assessments available. For investigator-reported response data, the date of PD for PFS and DOR will be the timepoint at which progression is first recorded. Analyses of best overall response, ORR, CRR, DOR, and PFS as reported by the investigator will be summarized as described in Sections [7.3](#) and [7.4](#).

For participants with bone marrow biopsy examination, date of bone marrow biopsy exam, exam adequacy, cellularity %, overall cellularity, bone marrow involvement of disease, immunohistochemistry testing, and bone marrow fibrosis score will be listed. For participants with bone marrow aspirate examination, date of bone marrow aspirate exam, exam adequacy, bone marrow aspirate results, bone marrow involvement of disease, cytogenetic analysis, and molecular analysis will be listed.

## 9. SAFETY AND TOLERABILITY

[Appendix A](#) provides a list of planned tables, figures, and listings. Sample data displays are included in a separate document.

### 9.1. General Considerations

Summary tables may be replaced with listings when appropriate. For instance, an AE frequency table may be replaced with a listing if it only contains a few unique PTs reported on relatively few participants.

### 9.2. Adverse Events

#### 9.2.1. Adverse Event Definitions

A TEAE is any AE either reported for the first time or worsening of a pre-existing event after the first dose of study drug and within 30 days of the last administration of study drug regardless of starting new anti-lymphoma therapy. Analysis of AEs (as discussed below) will be limited to TEAEs, but data listings will include all AEs regardless of their timing in relation to study drug administration. For purposes of analysis, all AEs will be considered TEAEs unless the AE can unequivocally be defined as not treatment-emergent.

Adverse events will be tabulated by MedDRA PT and SOC. Severity of AEs will be graded using the NCI CTCAE (v5.0; [NCI 2017](#)), Grades 1 through 5. The CTCAE reporting guidelines and grading details are available on the Cancer Therapy Evaluation Program website.

The subset of AEs considered by the investigator to be related to study drug will be considered treatment-related AEs. If the investigator does not specify the relationship of the AE to study drug, the AE will be considered treatment-related. The incidence of AEs and treatment-related AEs will be tabulated. In addition, serious TEAEs will also be tabulated.

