6.5.1. Supportive Care Guidelines for Diarrhea/Colitis

Participants should be informed to immediately report to the investigator any event of diarrhea. Treatment with piasalisib may be interrupted or modified according to the guidelines in [Table 7](#) to allow for resolution of diarrhea/colitis.

Participants should receive appropriate supportive care measures as deemed necessary by the investigator. For any Grade ≥ 1 diarrhea, participants should be advised to drink liberal quantities of clear fluids. If sufficient oral fluid intake is not feasible, fluid and electrolytes should be substituted via IV infusion. Participants should try to eat 5 to 6 small meals per day; low-fat, high-protein foods; and cooked instead of raw vegetables. Participants may supplement their diet with bananas, rice, applesauce, and toast to reduce the number of bowel movements and may also try crackers, gelatin, noodles, or oatmeal. Participants should avoid fried, fatty, greasy, or spicy foods; milk, milk products, and acidic drinks; high-fiber foods and foods that cause gas; and alcohol, caffeine, and herbal supplements ([Coutré et al 2015](#)).

For each occurrence, attempts should be made to rule out other causes, such as metastatic disease or bacterial or viral infection (including CMV), which might require additional supportive care.

It may be necessary to perform conditional procedures such as colonoscopy with biopsy as part of evaluation of the event. Note that several courses of steroid tapering may be necessary as symptoms may worsen when the steroid dose is decreased.

Participants should be carefully monitored for signs and symptoms of enterocolitis (such as diarrhea, abdominal pain or cramping, blood or mucus in stool, with or without fever) and of bowel perforation (such as peritoneal signs and ileus).

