7.1.1. Reasons for Discontinuation

Participants **must** be discontinued from study treatment for the following reasons:

- The participant has died.
- The participant has experienced an unacceptable toxicity defined as follows:
 - Occurrence of an AE that is related to study treatment that, in the judgment of the investigator or the sponsor's medical monitor, compromises the participant's ability to continue study-specific procedures or is considered to not be in the participant's best interest.
 - Persistent AE requiring a delay of therapy for more than 2 weeks (14 days) unless a greater delay has been approved by the sponsor.
- The participant is unable to tolerate study treatment.
- The participant has an objective radiographic tumor response of PD/PMD.
- Further participation would be injurious to the participant's health or well-being, in the investigator's medical judgment.
- The participant becomes pregnant.
- Informed consent is withdrawn. *Note:* Consent withdrawn means that the participant can no longer be followed. Participants may choose to discontinue study treatment and remain in the study to be followed for disease progression and survival per the schedule of assessments.
- The participant is considered lost-to-follow-up when they repeatedly fail to return for scheduled visits and is unable to be contacted by the study site (eg, after 3 telephone calls and/or a certified letter or local equivalent).
- The study is terminated by the sponsor.
- The study is terminated by the local health authority, IRB, or IEC.

Participants **may** be discontinued from study treatment in the following situation:

- If a participant is noncompliant with study procedures or study treatment administration in the investigator's opinion, then the sponsor should be consulted for instruction on handling the participant.

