8.8. Follow-Up

8.8.1. Safety Follow-Up

The safety follow-up period is the interval between the EOT visit and the scheduled follow-up visit, which should occur 30 to 35 days after the EOT visit (or after the last dose of study drug/treatment if the EOT visit was not performed). Adverse events and SAEs must be reported up until 1) at least 30 days after the last dose of study drug or the start of a new anti-lymphoma therapy or 2) until toxicities resolve, return to baseline, or are deemed irreversible. Reasonable efforts should be made to have the participant return for the follow-up visit and report any AEs that may occur during this period.

If a participant is scheduled to begin a new anti-lymphoma therapy before the end of the safety follow-up period, the safety follow-up visit should be performed before a new anti-lymphoma therapy is started. Once a new anti-lymphoma therapy has been initiated, the participant will move into the survival follow-up period.

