10.4.4.1. Adverse Events

Adverse events will be coded by the MedDRA dictionary and severity of AEs will be based on the NCI CTCAE v5.0 (NCI 2017) using Grades 1 through 5. A TEAE is any AE either reported for the first time or worsening of a pre-existing event after first dose of study treatment and within 30 days of the last administration of study drug.

Number (%) of participants reporting any TEAEs, any serious TEAEs, any Grade 3 or higher TEAEs, any treatment-related TEAEs, any treatment-related serious TEAEs, any treatment-related Grade 3 or higher TEAEs, any fatal TEAEs, and any TEAEs leading to treatment interruption/dose reduction/discontinuation will be tabulated by MedDRA system organ class and preferred term. Data listings will include all AEs regardless of their timing to study treatment administration.

Adverse events of special interest will be summarized as detailed in the Statistical Analysis Plan.

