#### 9.2.2. Adverse Events of Special Interest

The number of participants who experienced TEAEs of special interest listed below will be summarized by maximum severity.

- Colitis
- Diarrhea
- Exfoliative dermatitis
- Febrile neutropenia
- Rash
- Intestinal perforation
- Pneumonitis
- Pneumonia
- PJP infection
- CMV infection

- Herpes simplex
- Varicella zoster virus infection

The time to onset of a TEAE is defined as the interval between the date of first dose of study drug and the date of the first occurrence of a TEAE. Participants who have not experienced a TEAE at the time of analysis will be right-censored at the earlier of 30 days after the last dose date and date of last study visit through the end of safety follow-up. If participants have missing or partial last dose dates of study drug or onset date of a TEAE, the partial or missing dates will be handled using the rules explained in Section 4.1.4.

Summaries of time to onset of new or worsening Grade 3 or higher AEs will be provided using descriptive statistics and the life-table method for rash, colitis, diarrhea, febrile neutropenia, pneumonia, herpes simplex, and varicella zoster virus infection. In addition, summaries of time to onset of new or worsening AEs of any grade will be provided using descriptive statistics and the life-table method for colitis, diarrhea, exfoliative dermatitis, intestinal perforation, pneumonia, pneumonitis, PJP infection, CMV infection, herpes simplex, and varicella zoster virus infection. Kaplan-Meier plots of time to onset of new or worsening Grade 3 or higher AEs will be provided for rash, colitis, and diarrhea. In addition, Kaplan-Meier plots of time to onset of new or worsening AEs of any grade will be provided for colitis and diarrhea.

Descriptive statistics of time to onset of these TEAEs of special interest are based on all participants who have experienced a TEAE at the time of analysis. To summarize these TEAEs of special interest using the life-table method, the effective sample size is defined as the number of participants at the beginning of interval minus half the participants censored in the interval. The conditional proportion is calculated as the number of first events divided by the effective sample size in the interval.

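### AE tables stop 30 days after the last dose while AE collection runs to the safety visit after EOT, so after a dose hold later AEs reach only the listings; a supplementary count would show them

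*SAP*

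**What the plan says.** **Analysis window.** SAP 9.2.1 counts an AE as treatment-emergent if it starts or worsens after the first dose and "within 30 days of the last administration of study drug regardless of starting new anti-lymphoma therapy". Protocol 10.4.4.1 has the same limit: "within 30 days of the last administration of study drug". SAP 9.2.1 adds that "Analysis of AEs (as discussed below) will be limited to TEAEs", while "data listings will include all AEs regardless of their timing in relation to study drug administration". In SAP 9.2.2, participants without the event are "right-censored at the earlier of 30 days after the last dose date and date of last study visit through the end of safety follow-up" in the time-to-onset analyses.

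**Collection period.** Protocol 8.8.1 defines safety follow-up as the interval from the EOT visit to a visit "which should occur 30 to 35 days after the EOT visit", or the same number of days after the last dose if no EOT visit took place, and asks for AEs arising in that interval. The schedule of activities places an AE assessment at that visit. Protocol 9.3 uses the same anchor for final safety follow-up, and Protocol 9.4 requires SAEs to be reported through the last safety visit or until new anticancer therapy. The 30 days after the last dose in Protocol 8.3.1 is a minimum, cut short by new anti-lymphoma therapy.

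**Why the two anchors can separate.** Under Protocol 8.7 the EOT visit follows permanent discontinuation, not the last dose. One of the mandatory reasons to discontinue in Protocol 7.1.1 is "Persistent AE requiring a delay of therapy for more than 2 weeks (14 days) unless a greater delay has been approved by the sponsor". For diarrhea and colitis, Protocol 6.5.1 warns that "several courses of steroid tapering may be necessary as symptoms may worsen when the steroid dose is decreased".

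**The concern.** The analysis clock starts at the last tablet and the collection clock at the EOT visit. For a participant whose drug is interrupted for toxicity and never restarted, the first can run out well before the second. An infection, perforation or death with onset at, say, day 38 after the last dose would be reported by the site and recorded, yet would not count as a TEAE.

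The participants most exposed to this are those held for a persistent toxicity, some of them on steroids. The Protocol itself treats infection risk as outlasting 30 days: PJP prophylaxis continues for 2 to 6 months after the last dose. PJP, CMV infection, colitis and intestinal perforation are all AEs of special interest. With about 40 participants, one omitted participant changes an incidence by 1/40 = 2.5 percentage points, and the serious, fatal and AESI tables may contain only a few. The omission can only lower the counts.

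**Working it through.** The plan gives no figure on this point to reproduce. The check is day arithmetic on its own rules.

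**Inputs**
- End of TEAE window and latest AE onset censoring: last dose + 30 days (SAP 9.2.1 and 9.2.2, Protocol 10.4.4.1).
- Safety follow-up visit: EOT visit + 30 to 35 days (Protocol 8.8.1).
- Lag from last dose to EOT visit: h days. The documents give no distribution for h and no maximum, so the values below are assumptions. A delay of more than 14 days (Protocol 7.1.1) implies h of at least 15 in whole days when that is the route to discontinuation.

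**Formulas**, with the last dose as day 0
- Safety visit: day h + 30 to day h + 35.
- Collected days outside the window: (h + 30) − 30 = h, up to (h + 35) − 30 = h + 5.
- Share of the post-dose collection period: h/(h + 30) to (h + 5)/(h + 35).

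| Lag h (assumed) | Safety visit, days after last dose | Collected days outside the window | Share of post-dose days |
|---|---|---|---|
| 0 | 30–35 | 0–5 | 0–14% |
| 7 | 37–42 | 7–12 | 19–29% |
| 14 | 44–49 | 14–19 | 32–39% |
| 15 | 45–50 | 15–20 | 33–40% |
| 21 | 51–56 | 21–26 | 41–46% |
| 28 | 58–63 | 28–33 | 48–52% |

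For example, at h = 14: 14/44 = 32% and 19/49 = 39%. At h of 31 or more, which needs a sponsor-approved extension, the window has closed before the EOT visit and all of safety follow-up lies outside it. If no EOT visit is held, the safety visit is counted from the last dose and the gap is 0 to 5 days.

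**Where an AE dated in the gap appears**
- *Left out:* the TEAE tables (3.2.x), including the Grade 3 or higher, serious, fatal and AESI tables, and the AESI time-to-onset summaries, life tables and Kaplan-Meier plots.
- *Kept:* listings 2.7.x. A death still counts in overall survival (SAP 7.4.4).
- *Not cut at 30 days:* laboratory onset for ALT, AST and neutrophils, which SAP 9.3.4 censors at the last graded visit.
- *Still counted:* the toxicity that led to the hold, because it began on treatment.

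SAP 9.2.1 treats an AE as a TEAE unless it is clearly not one. That default helps when the date is ambiguous. It does not help an AE with a known onset after day 30.

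**The case against.** A window of last dose + 30 days is a conventional choice. It matches the minimum collection period in Protocol 8.3.1, and Protocol and SAP agree on it. This stands: the SAP does not depart from the Protocol, and the mismatch is between collection and analysis.

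A reader might infer that every toxicity discontinuation puts the EOT visit at least 14 days after the last dose. The documents do not support that. The prolonged delay is one of several routes in Protocol 7.1.1. Table 7 calls for discontinuation with no preceding hold for pneumonitis of Grade 2 or higher, exfoliative dermatitis of Grade 2 or higher, intestinal perforation and other Grade 4 toxicity. Suspected PJP is interrupted and then stopped once confirmed, with no 14-day period.

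A reader might also infer that late AEs vanish from the safety report. They do not: the listings cover all, serious, Grade 3 or higher, fatal and related AEs, and in a study of about 40 participants listings are readable. Nor is every death after day 30 missed by the fatal table. It counts TEAEs with a fatal outcome, so an event that began inside the window and proved fatal later can still be included. The text is unsettled for worsening: Protocol 9.3 records each severity change as a separate AE, while Protocol 9.4 reports progression of an SAE as follow-up to the original event.

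SAP 9.2.2 censors the duration of unresolved nonserious AEs at the later of the safety visit and EOT + 35 days. That does not prove an error in the onset rule, since an event already under way may reasonably be followed longer than the window for new events.

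Lastly, moving the TEAE limit outright to the later of 30 days and EOT + 35 days would do harm. It would keep participants at risk in the onset curves after collection had stopped for new anti-lymphoma therapy or a missed visit, which lowers the apparent rates. That objection succeeds against replacing the definition. It does not succeed against adding a second count: listings hold the late AEs, but no planned table counts them.

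**Conclusion.** The mismatch is real and limited. For participants discontinued after a dose hold, AEs are collected for h to h + 5 days beyond the end of the TEAE window, and new or worsened AEs dated there reach only the listings. At an assumed lag of 14 days the gap is 14 to 19 days; without a lag it is at most 5.

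The 32% to 39% at that lag is a share of post-dose calendar days for one assumed participant. It must not be read as a share of events lost. The documents do not give the number of participants with a long lag or of AEs in the gap, so the effect on any table is unknown and may be nil. Its direction is known: TEAE counts can only be lower than counts over the full collected period.

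The conclusion assumes that an EOT visit takes place after the decision to discontinue, that sites report AEs through the safety visit as Protocol 8.8.1 asks, and that new anti-lymphoma therapy has not already ended collection. The documents do not support calling the 30-day definition wrong. They do support a supplementary count as a cheap improvement that could change the reported AESI, serious and fatal figures.

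**What to change.** Keep the 30-day TEAE definition as the main analysis, so that results remain comparable with other studies.

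1. In SAP 9.2.1 to 9.2.3, add a second column or a supplementary table for the overall, Grade 3 or higher, serious, fatal and AESI summaries. Count all AEs with onset or worsening from the first dose through the safety follow-up visit, or through the last AE assessment if that visit was missed. Stop at the start of new anti-lymphoma therapy where AE collection stops.
2. In SAP 9.2.2, add a supplementary AESI time-to-onset analysis censored at the last date on which AEs were actually collected. Do not use EOT + 35 days as a stand-in when the visit was missed.

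This needs one derived date per participant and a few extra outputs, all from data already collected. It changes no dosing or clinical rule. The downsides are slightly higher supplementary counts and a window whose length varies between participants, which a table footnote should state.

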#### 9.2.2. Adverse Events of Special Interest

The number of participants who experienced TEAEs of special interest listed below will be summarized by maximum severity.

- Colitis
- Diarrhea
- Exfoliative dermatitis
- Febrile neutropenia
- Rash
- Intestinal perforation
- Pneumonitis
- Pneumonia
- PJP infection
- CMV infection

- Herpes simplex
- Varicella zoster virus infection

The time to onset of a TEAE is defined as the interval between the date of first dose of study drug and the date of the first occurrence of a TEAE. Participants who have not experienced a TEAE at the time of analysis will be right-censored at the earlier of 30 days after the last dose date and date of last study visit through the end of safety follow-up. If participants have missing or partial last dose dates of study drug or onset date of a TEAE, the partial or missing dates will be handled using the rules explained in Section 4.1.4.

Summaries of time to onset of new or worsening Grade 3 or higher AEs will be provided using descriptive statistics and the life-table method for rash, colitis, diarrhea, febrile neutropenia, pneumonia, herpes simplex, and varicella zoster virus infection. In addition, summaries of time to onset of new or worsening AEs of any grade will be provided using descriptive statistics and the life-table method for colitis, diarrhea, exfoliative dermatitis, intestinal perforation, pneumonia, pneumonitis, PJP infection, CMV infection, herpes simplex, and varicella zoster virus infection. Kaplan-Meier plots of time to onset of new or worsening Grade 3 or higher AEs will be provided for rash, colitis, and diarrhea. In addition, Kaplan-Meier plots of time to onset of new or worsening AEs of any grade will be provided for colitis and diarrhea.

Descriptive statistics of time to onset of these TEAEs of special interest are based on all participants who have experienced a TEAE at the time of analysis. To summarize these TEAEs of special interest using the life-table method, the effective sample size is defined as the number of participants at the beginning of interval minus half the participants censored in the interval. The conditional proportion is calculated as the number of first events divided by the effective sample size in the interval.

The longest duration of a TEAE of any grade is defined as the longest interval between the date of occurrence of a TEAE and the date of resolution. The longest duration of a Grade 3 or higher TEAE is defined as the longest interval between the date of occurrence of a Grade 3 or higher TEAE and the date of improvement to Grade 2 or lower. If participants have missing or partial onset/end date of a TEAE, the partial or missing dates will be handled using the rules explained in Section 4.1.4. Participants who have missing end date of a TEAE at the time of analysis will be right-censored using the following algorithm:

- If the TEAE is serious, then the participant will be censored at the earlier date of data cutoff, study discontinuation, and death.
- If the TEAE is not serious,
  - If the participant is ongoing with study treatment, then the participant will be censored at the data cutoff date, OR
  - If the participant discontinued treatment, then the participant will be censored at date of safety follow-up visit, or 35 days after the end of treatment visit (or after the last dose if the end of treatment visit was not performed), whichever is later; the censored date will be truncated by the earlier date of data cutoff, study discontinuation, and death if beyond.

Longest duration of new or worsening Grade 3 or higher colitis, diarrhea, rash, and febrile neutropenia will be summarized. In addition, longest duration of new or worsening AEs of any grade will be summarized for colitis, diarrhea, and rash.

The total number of participants whose TEAE of any grade resolved or whose Grade 3 or higher TEAE improved to Grade 2 or lower and the number of participants censored will be summarized. The Kaplan-Meier estimate of median time to resolution/improvement and its 95% CIs will be provided, with the CIs calculated using the generalization of Brookmeyer and Crowley's method (1982) with log-log transformation (Klein and Moeschberger 1997). Resolution/improvement rates at selected timepoints will also be provided with 95% CIs calculated using Greenwood's formula to estimate the standard error.

TEAEs of special interest to be summarized may be adjusted based on emerging data.

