### **9.3.4. Worsening Laboratory Events of Special Interest**

Laboratory events of special interest are listed below.

- ALT increased
- AST increased
- Absolute neutrophil count decreased

The time to onset of a worsening laboratory event is defined as the interval between the date of first dose of study drug and the date of the first occurrence of CTC grade worse than baseline for the laboratory event. Participants who have not experienced a worsening laboratory event at the time of analysis will be right-censored at the last postbaseline study visit with nonmissing CTC grade of the laboratory event.

Time to onset of worsening Grade 3 or 4 laboratory events of special interest will be summarized using descriptive statistics and the life-table method as described in Section 9.2.2, and the Kaplan-Meier plot of time to onset of worsening Grade 3 or 4 absolute neutrophil count decreased will be provided. Laboratory events of special interest to be summarized may be adjusted based on emerging data.

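### The AESI onset curves in SAP 9.2.2 censor death and closure of the TEAE window, so one minus Kaplan-Meier overstates the proportion affected; a cumulative incidence curve should be added

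*SAP*

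**What the plan says.** SAP 9.2.1 counts an event as a TEAE only if it starts or worsens after the first dose and "within 30 days of the last administration of study drug regardless of starting new anti-lymphoma therapy". SAP 9.2.2 defines time to onset from first dose to first occurrence. A participant without the event "will be right-censored at the earlier of 30 days after the last dose date and date of last study visit". Death and permanent discontinuation have no status of their own.

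Three kinds of onset output follow in SAP 9.2.2:

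- **Plots.** The SAP states that "Kaplan-Meier plots of time to onset of new or worsening Grade 3 or higher AEs will be provided for rash, colitis, and diarrhea", and that "Kaplan-Meier plots of time to onset of new or worsening AEs of any grade will be provided for colitis and diarrhea". That makes five curves, listed together as Figure 4.5.1 in Appendix A.
- **Life table (Table 3.2.28).** Here "the effective sample size is defined as the number of participants at the beginning of interval minus half the participants censored in the interval". The only quantity defined from it is per interval: "The conditional proportion is calculated as the number of first events divided by the effective sample size in the interval".
- **Descriptive statistics (Table 3.2.27)**, restricted to participants who had the event.

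Separately, Table 3.2.26 counts participants with each AESI by maximum severity.

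For laboratory events, SAP 9.3.4 says that participants without a worsening event "will be right-censored at the last postbaseline study visit with nonmissing CTC grade of the laboratory event". It plans a Kaplan-Meier plot for Grade 3 or 4 neutrophil count decrease. No 30-day window is stated there.

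Neither SAP section 9 nor the lists in Appendix A contain a cumulative incidence function or any other competing-risk method. Protocol 10.4.4.1 leaves AESI summaries to the SAP.

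**The concern.** Censoring in a Kaplan-Meier estimate assumes that the censored person could still have the event later, at the same rate as those who remain. That is reasonable for someone on treatment at data cutoff. It is not true of someone who has died, or whose TEAE window closed 30 days after the last dose, because by the SAP's own definition a first TEAE can then no longer occur. The estimator passes their risk on to those still treated, and one minus the curve rises above the proportion who actually have the event.

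Such exits are part of the design. Protocol 7.1.1 requires discontinuation at progression, unacceptable toxicity and death. Under Protocol Table 7 some AESIs, such as pneumonitis of Grade 2 or higher and intestinal perforation, lead to permanent discontinuation, so one AESI can censor a participant on another AESI's curve. Protocol 6.5.3 reports that most immune-related events come after the first 9 weeks, which leaves time for an exit to come first.

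At stake is how the toxicity curves are read. The report would show a crude percentage and a higher curve for the same event, with nothing to explain the difference.

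**Working it through.** **What the documents supply.** There are about 40 participants and about 1 year of accrual (Protocol 4.2), and the last patient is followed for 12 months (SAP 7.3). Protocol 2.1.3 gives 36% any-grade diarrhea/colitis in an earlier study. That population and regimen were different and no timeframe is attached, so it serves only as an anchor. The documents give no AESI risk, discontinuation rate or death rate for this trial, so there is no planned figure to reproduce. All rates below are assumptions.

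**Formulas.** Let h be the constant monthly hazard of the AESI and d the constant hazard of an exit (death or window closure). Then:

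- One minus Kaplan-Meier tends to 1 − exp(−h·t).
- The true cumulative incidence is h/(h+d) × [1 − exp(−(h+d)·t)].

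The first exceeds the second whenever d > 0.

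**Check 1: 36% true incidence at 18 months, varying the median time to exit.** For a median of 8 months, d = ln 2/8 = 0.0866. Solving for 36% at 18 months gives h = 0.0554. At 12 months:

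- 1 − exp(−0.0554 × 12) = 48.6%.
- 0.0554/0.1421 × [1 − exp(−0.1421 × 12)] = 31.9%.

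| Median time to exit (months) | 1−KM, 12 mo | True, 12 mo | Excess (points) | Excess in KM standard errors, N=40 | 1−KM, 18 mo (true 36%) |
|---|---|---|---|---|---|
| 8 | 48.6% | 31.9% | 16.7 | 1.5 | 63% |
| 12 | 40.6% | 30.2% | 10.4 | 1.1 | 54% |
| 16 | 36.7% | 29.2% | 7.5 | 0.8 | 50% |
| 24 | 32.9% | 28.1% | 4.8 | 0.6 | 45% |

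**Check 2: rarer events, same model and same four medians.** The 12-month excess, in standard errors, is:

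- 10% event at 18 months: 0.67, 0.49, 0.39, 0.28.
- 5% event at 18 months: 0.47, 0.34, 0.27, 0.19.

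Seven of these eight values are under half a standard error.

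**Check 3: fixing the 12-month incidence instead.** Exit probabilities by 12 months are set at 20%, 40% and 60%.

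| True incidence at 12 mo | 1−KM, 20% exit | 1−KM, 40% exit | 1−KM, 60% exit |
|---|---|---|---|
| 10% | 11.1% | 12.7% | 15.1% |
| 20% | 22.2% | 25.2% | 29.7% |
| 36% | 39.8% | 44.8% | 52.1% |

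**Check 4: simulation with the 30-day tail.** This used 3,000 trials of 40 participants with 12 to 24 months of follow-up. The window closed 30 days after the last dose or at death, and life-table intervals were 3 months. The monthly AESI hazards were 0.012, 0.035 and 0.05. The 12-month discontinuation probabilities were 20, 40 and 60%, and the 12-month death probabilities 3, 5 and 10%.

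| Scenario | 12 mo: 1−KM / cumulative life table / Aalen-Johansen | 24 mo: same order |
|---|---|---|
| Low | 13.3 / 13.3 / 12.0% | 24.3 / 24.1 / 19.8% |
| Mid | 34.2 / 34.1 / 27.7% | 54.6 / 53.9 / 37.7% |
| High | 45.1 / 44.9 / 31.8% | 63.9 / 62.8 / 37.0% |

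At 12 months the Aalen-Johansen estimate equals the crude proportion in all three scenarios. A cumulative life-table figure, if shown, carries nearly the same excess as Kaplan-Meier.

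**Check 5: the life-table quantity the SAP does define.** With 40 at risk, 4 events and 10 exits in an interval, the conditional proportion is 4/(40 − 10/2) = 4/35 = 11.4%. Keeping the exits in the denominator gives 4/40 = 10.0%. The shift is small.

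**The case against.** The best defence is that these outputs target a different quantity. SAP 9.2.2 calls them time to onset and plans no onset rate at fixed months, whereas SAP 7.4.3, 7.4.4 and the resolution analysis in 9.2.2 ask for rates at timepoints explicitly. Risk among those still exposed is a legitimate question for late toxicity. A cumulative incidence curve has its own weakness: it depends on how long people stay on treatment, so a drug stopped early for progression can look safer. The proportion affected is already available from Table 3.2.26.

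Much of this stands, and it rules out replacing the Kaplan-Meier curves. It does not remove the point. The SAP never says that the curves are hypothetical on-treatment risk. That reading needs independent censoring, which is doubtful when progression and other toxicities cause the exits. An unlabelled curve invites the ordinary reading.

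A reader might also infer more than the documents support:

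- **That all tabulated AESI risk is overstated.** The crude counts and the descriptive onset statistics do not use this censoring, and the interval proportions barely move. No cumulative life-table column is specified, and the shells are in a separate document.
- **That discontinuation itself makes a later AESI impossible.** SAP 9.2.1 leaves 30 days after the last dose; only death closes the window at once.
- **That every exit before cutoff is a competing event.** Loss to follow-up and withdrawal of consent to follow-up are ordinary censoring, because the event may happen unseen.
- **That the argument carries over unchanged to SAP 9.3.4.** Laboratory events are censored at the last graded visit, with no stated window. Nor do the documents say that neutropenia comes late: Protocol 6.5.3 concerns immune-related events.

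**Conclusion.** The point holds in a limited form. For the five AESI onset curves, one minus Kaplan-Meier overstates the probability of having the AESI as a TEAE whenever a death or window closure precedes a later onset. The direction follows from the censoring rule and the TEAE definition. The size does not follow from the documents.

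Under the assumed rates the excess at 12 months runs from about 1 to 17 points and grows with follow-up. The upper end needs a 36% event and a median of 8 months to exit. Three of the five curves are for Grade 3 or higher events; if those occur in 5 to 10% of participants, the excess is mostly under half a standard error. Constant hazards are a simplification, and early onset or few discontinuations would shrink the gap.

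The severity is minor. These are descriptive single-arm displays with no formal tests (SAP 3.2), and neither the ORR analysis nor the futility rule is touched.

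**What to change.** In SAP 9.2.2 and Figure 4.5.1:

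1. Add an Aalen-Johansen cumulative incidence curve to each of the five AESI onset plots. The competing events are death without the AESI, and the end of the 30-day TEAE window after permanent discontinuation without the AESI.
2. Censor only participants who at data cutoff are still on treatment or within the 30-day window, those lost to follow-up, and those who withdrew consent. A participant who stops treatment by choice but stays in follow-up counts as a permanent discontinuation.
3. Use the Aalen-Johansen curve for any statement of the proportion affected by a given month. If Table 3.2.28 shows a cumulative column, apply the same rule there; the interval conditional proportions can stay.
4. Keep the Kaplan-Meier curves for cross-study comparison, labelled as hypothetical on-treatment risk under independent censoring.

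For the neutrophil plot in SAP 9.3.4 (Figure 4.6.2), treat at least death as a competing event and label the Kaplan-Meier curve in the same way.

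The cost is SAP wording, a little programming and one extra curve per plot. No new data are needed.
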